### 1.6 Physiological changes of the cardio—circulatory system during transition

The main difference of fetal cardio-circulation to the cardio-circulation after birth is that before birth the lungs are by-passed, and the oxygenated blood is provided by the placenta. The three bypasses are the ductus venosus (DV), a connection between the umbilical vein and the vena cava inferior, the ductus arteriosus (DA), a vessel between pulmonary artery and the aorta to avoid pulmonary circulation, and the foramen ovale (FO), a connection between the cardiac atria which also serves the purpose to bypass the pulmonary circulation.

Due to these described peculiarities the fetal circulation is a parallel circulation instead of a serial one (32, 33).

During transition, the pulmonary resistance drops, due to the lung aeration. This resistance-drop triggers an increase of the pulmonary blood-flow. Considering this new detour, depending on when the umbilical cord was clamped, the preload is reduced during the first minutes after birth. Furthermore, due to the cord clamping the low-resistance placenta circulation is yield, which leads to an increased afterload and the arterial pressure increases. As a result of reduced preload and initial-increased afterload, the cardiac output is reduced with clamping the cord.

Considering these changes, the cerebral blood-flow as well as the systemic blood flow and systemic blood pressure are initially increased whereby a drop occurs immediately after the initial increase due to the reduced cardiac output (34). Afterwards, the cardiac output continues to stay low until the pulmonary blood-flow increases with ventilation of the lungs (35). During this cardio-circulatory and pulmonary changes immediately after birth the cerebral autoregulatory mechanisms should maintain the cerebral blood-flow constant. These autoregulatory mechanisms are not yet fully comprehensible especially in preterm neonates (36, 37).

In term neonates Baik et al have demonstrated that cFTOE as well as crSO2 are independent of MABP (38, 39). However, Baik's study (38) only investigated MABP in connection with crSO2 as well as cFTOE 15 minutes after birth. However, the question remains, if in term neonates MABP has some influence on cerebral oxygenation before minute 15 after birth when the lung is aerated, and most cardio-circulatory changes take place.

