Furthermore, Baik's study (38) showed a significant negative correlation between MABP and cFTOE in preterm neonates which seems to suggest that in preterm infants the autoregulatory mechanism are less mature than in term neonates and that preterm neonates may benefit from blood pressure monitoring during immediate neonatal transition. These findings are in accordance with the animal model of Helou and Rhees observation in neonates (15–17). However again the question remains, if in preterm neonates MABP has more influence on cerebral oxygenation before minute 15 after birth when the lung is aerating and most cardio-circulatory changes take place.

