## 2. Term neonates ( $\geq 37+0$ weeks of gestation)

## 5 Sample size

In preterm infants, it was found that the correlation between MABP, and cFTOE is  $r = -0.19$  at 15 minutes after birth. Even lower correlations were found for crS02 and MABP and for term infants (38). Due to the bevor in 1.6. described changes during the immediate transition period, which lead to a decrease in cardiac preload and an increase in cardiac afterload the cardiac output is reduced. Considering these changes in the cerebral blood flow as well as the systemic blood flow and systemic blood pressure we expect to find higher correlations in the fifth and tenth minute after birth. According to our experience, it is feasible to include 50 infants in this study. If 50 infants are included and a drop-out rate of 10% is considered, 45 infants can be analyzed. Using these 45 infants the lower limit of Spearman's rank correlation coefficient's 95% CI will be 0.14 for a correlation coefficient of  $r = 0.40$ . This lower limit increases to 0.20, 0.26, 0.32 for  $r = .45$ ,  $r = .50$  and  $r = .55$  respectively.

Therefore we aim for a sample size of 50 neonates in each group – preterm neonates and term neonates, resulting in a total sample size of 100 neonates

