## 14 Data analysis

Initially, all data will undergo a descriptive analysis to uncover any data anomalies and missing values that may impact the validity of the data analysis.

Demographic, NIRS and routine monitoring data will be presented as n (%), mean and standard deviation (SD), or median and interquartile range (IQR), as appropriate.

Comparisons of categorical characteristics between preterm and term infants will be performed using chi-square test and for continuous variables using t-test or Mann-Whitney U-test, as appropriate.

Correlation analyses will be performed to investigate, if there is a connection between crSO2, cFTOE and MAP in preterm and term infants at different time points, individually. Correlations will be performed using Spearman's rank correlation coefficient or Pearson's correlation when appropriate. A p-value < 0.05 will be considered statistical significant. The statistical analyses will be performed using IBM SPSS Statistics 22.0.0 (IBM Corporation; Armonk, USA).

Comparison of correlation analyses at different time points and in term and preterm neonates will be descriptive. Statistical analysis is planned to be performed in cooperation with the Institute for Medical Informatics, Statistics and Documentation, Medical University of Graz, Austria.

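### Preterm infants: the plan asks whether blood pressure matters more before minute 15, but gives the difference between minutes no measure of uncertainty and no common set of infants

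*Combined protocol and SAP*

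**What the plan says.** **Rationale.** Section 1.6 of the combined protocol and SAP notes that the earlier study looked only at minute 15. For preterm infants it leaves open "if in preterm neonates MABP has more influence on cerebral oxygenation before minute 15 after birth". For term infants the question is weaker: "if in term neonates MABP has some influence on cerebral oxygenation before minute 15 after birth".

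**Expectation.** Section 5 cites the earlier preterm result for MABP and cFTOE, "cFTOE is $r = -0.19$ at 15 minutes after birth", says that crSO2 and term infants showed even lower correlations, and adds that "we expect to find higher correlations in the fifth and tenth minute after birth".

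**Measurements.** Section 9.1 lists blood pressure, NIRS and FTOE at minutes 5, 10 and 15, all as primary.

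**Analysis.** Section 14 plans a separate correlation for each time point in each group, with p < 0.05 as the criterion. On comparing them it says only: "Comparison of correlation analyses at different time points and in term and preterm neonates will be descriptive". It plans no difference between coefficients, no interval for one, and no repeated-measures model. Missing values are to be looked for in a descriptive step, but nothing says which infants enter a comparison of two minutes.

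**The concern.** In preterm infants, *more* and *higher* are comparisons with minute 15. To answer them one needs the difference between the early and the minute-15 coefficient, and how uncertain that difference is. The plan supplies the two coefficients and two p-values, and leaves the rest to the eye.

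Two errors then become easy. First, a coefficient that is significant at minute 5 but not at minute 15 may be read as a time effect, although the contrast between a significant and a non-significant result is not itself evidence of a difference. Second, if some infants lack a reading at one of the minutes, the two coefficients describe different infants, and a change in who was measured can look like a change over time. The comparison that motivates the preterm part of the study could be asserted or dismissed without support.

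**Working it through.** **Inputs from the documents**
- Infants per group: "If 50 infants are included and a drop-out rate of 10% is considered, 45 infants can be analyzed" (50 × 0.9 = 45).
- Correlation at minute 15: absolute size 0.19 (section 5; preterm, MABP with cFTOE).
- Early correlation: 0.40, the lowest of the four illustrative values in section 5 (0.40 to 0.55).
- Significance level 0.05 (section 14). Sidedness is not stated; two-sided is assumed.

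**Assumptions the documents do not supply**
- ρ, the correlation of an infant's own readings between two minutes, is varied from 0 to 0.7 (0.9 in step 4) and taken as equal for MABP and for the oxygenation measure.
- MABP at one minute correlates with oxygenation at the other by ρ times the mean of the two same-minute correlations.
- Data are multivariate normal. Correlations are given as absolute sizes; for cFTOE the signs reverse.

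**Step 1. The plan's own figures.** Section 5 states: "Using these 45 infants the lower limit of Spearman's rank correlation coefficient's 95% CI will be 0.14 for a correlation coefficient of" 0.40, and then "This lower limit increases to 0.20, 0.26, 0.32 for" 0.45, 0.50 and 0.55. The Fisher formula is tanh(atanh(r) − 1.96/√(n − 3)).
- n = 45: 1.96/√42 = 0.302, and atanh(0.40) − 0.302 = 0.424 − 0.302 = 0.121 before rounding the terms, so the limit is 0.12. The other three are 0.18, 0.24 and 0.31.
- n = 50: 1.96/√47 = 0.286, giving 0.14, 0.20, 0.26 and 0.32.

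The stated limits thus match 50 infants, before drop-out, not 45. That is a side remark. What matters here is that they describe a single coefficient and never a difference between two.

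**Step 2. What a by-eye reading would see.** With n = 45, the smallest significant coefficient is 2.017/√(43 + 2.017²) = 0.29. An observed 0.40 is significant and 0.19 is not. Yet the separate 95% CIs, 0.12 to 0.62 and −0.11 to 0.46, overlap widely.

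**Step 3. No time effect: true correlation 0.19 at both minutes.** Simulated Spearman coefficients, 45 paired infants, 20,000 studies per row:

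| ρ | SD of difference | Differ by more than 0.20 | Only one minute significant |
|---|---|---|---|
| 0 | 0.21 | 34% | 34% |
| 0.3 | 0.20 | 31–32% | 32% |
| 0.5 | 0.18 | 27% | 30% |
| 0.7 | 0.15 | 20% | 25% |

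Check by normal approximation, with unrounded SDs of 0.209 and 0.155: 2 × [1 − Φ(0.20/0.209)] = 34% and 2 × [1 − Φ(0.20/0.155)] = 20%.

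**Step 4. A real time effect: 0.40 early, 0.19 at minute 15.** At ρ = 0.5, 95% of simulated differences fall between about −0.14 and 0.54 (repeat runs vary by 0.01).

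The large-sample calculation for dependent correlations agrees. At ρ = 0 the difference on the Fisher scale is 0.424 − 0.192 = 0.231 (before rounding the terms), with SE √(2/42) = 0.218. The ratio is 1.06, and power is Φ(1.06 − 1.96) plus a negligible tail, about 19%. Over the range of ρ:

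| ρ | 95% CI for a difference of 0.21 | Power |
|---|---|---|
| 0 | −0.17 to 0.59 | 19% |
| 0.5 | −0.12 to 0.54 | 23% |
| 0.7 | −0.06 to 0.48 | 32% |
| 0.9 | 0.05 to 0.37 | 71% |

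For 80% power, about 297, 222 or 151 infants per group would be needed at ρ = 0, 0.5 or 0.7.

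**The case against.** **The formal question contains no time contrast.** This stands. The primary aim (2.1) and Primary Hypothesis I (3.1) ask for an association within 15 minutes. A reader might infer that early versus minute 15 is the study's primary question in both groups; the documents do not support that. The comparative wording is in the preterm rationale and in section 5. The term question, whether there is some early influence, is answered by the separate coefficients at minutes 5 and 10.

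**The sample size does not depend on the contrast.** Also true. Section 5 takes 50 per group from feasibility and states no size of difference. The 0.40 used above is an illustrative value from that section, not a target.

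**Each minute gets its own coefficient.** Yes, so the point difference is visible. It would be too strong to say that the question gets no estimate. What is missing is the uncertainty and the common set of infants.

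**Nothing says the infants will differ between minutes.** Correct. One might infer from section 7.3, where the NIRS sensor goes on once the infant reaches the desk, that minute-5 readings will be missing more often. The protocol does not say so. The point is only that no rule guards against it.

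**It is a pilot and the descriptive comparison is declared.** Fair, and the plan nowhere says that it will read significance at one minute only as a time effect. But a descriptive comparison still informs the reader better with an interval than without.

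**A claim rule based on intervals would be no better.** This stands too. Two groups, two outcomes and two contrasts give eight intervals. In a simulation with no true time difference, at least one excluded zero in 20–29% of studies (|r| = 0.19, assumed between-minute correlation 0.3 or 0.7, assumed crSO2–cFTOE correlation −0.7 or −0.9, 400 studies per setting). With the low power in step 4, this argues for reporting intervals without a claim rule.

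**Conclusion.** The point holds for preterm infants as a gap in reporting. It is not a flaw in the primary analysis. The protocol raises an early-versus-minute-15 comparison that section 14 leaves without any measure of uncertainty and without a paired set of infants. With 45 infants and no time effect, coefficients more than 0.20 apart occur in about 20–34% of studies, and significance at only one of the two minutes in about 25–34%.

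These sizes rest on the assumed between-minute correlation (0.7 down to 0), the cross-minute assumption and normality. They also rest on 0.19, which the protocol cites for MABP and cFTOE in preterm infants only. For crSO2 and for term infants the cited correlations are lower, so the figures are indicative there.

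**What to change.** In section 14, keep the comparison of minutes exploratory and add:
- the difference in Spearman coefficients, minute 5 minus 15 and minute 10 minus 15, for cFTOE and crSO2, primarily in preterm infants and as supportive information in term infants;
- restriction of each difference to infants with paired data at both minutes, with n given at each minute;
- a 95% bootstrap CI that resamples whole infants, so that the dependence between minutes is kept;
- the direction that means a stronger early influence under the hypothesis: positive for crSO2, negative for cFTOE;
- a statement that the intervals are not adjusted for multiplicity and support no confirmatory claim;
- a statement that significance at one minute but not at another will not be read as a time effect.

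The cost is a short paragraph and a bootstrap on data already being collected, with no extra infants or procedures. The downside is that the intervals will be wide and will often leave the contrast unresolved, which the report should then say.
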